10.3 Data Management

All required data for this clinical study will be recorded via a validated database. This database complies with GCP requirements, laws and regulations applicable to the conduct of clinical trials, ISO 14155, and 21 CFR 11 (US Code of Federal Regulations) pertaining to the use of electronic records and signatures. System training for all research coordinators and Investigators will be conducted through instructor-led training supported with an on-line training module.

Incoming data will be frequently reviewed to identify inconsistent or missing data and any adverse events. Investigators are responsible for the accurate completion and timely submission of the data collected during this trial. Any data issues are to be promptly addressed with the Investigator by the study manager, designated monitor/CRO and/or Sponsor.

Clinical procedures have been established to ensure that complete, accurate and timely data are submitted, that protocol requirements are followed and that adverse events are correctly reported and investigated. Investigators are to maintain all source documents as required by the protocol, including laboratory results, supporting medical records and signed Informed Consent forms. The source documents will be verified during regular monitoring visits to ensure that the clinical data is complete and accurate.

10.4 Adverse Events & Definitions

A complication is defined as any clinical finding that has the potential to become clinically significant in the opinion of the investigator. A complication may progress in the level of clinical significance and become classified as an adverse event. All complications shall be recorded on the CRFs.

Adverse Events (AEs) are clinical findings that result in an untoward medical event.

Please record all AEs on the CRFs. Adverse Events will be further classified as Serious Adverse Events (SAEs) if the event:

- Is life threatening or fatal;
- Results in permanent impairment of a body structure or function;
- Results in congenital anomalies/birth defects
- Requires or prolongs hospitalization; or
- Requires medical or surgical intervention to preclude permanent impairment of a body function or permanent damage to a body structure.

Note: Hospitalization is defined as any initial admission (even if less than 24 hours) to a healthcare facility as a result of a precipitating clinical adverse effect; to include transfer within the hospital to an intensive care unit. Hospitalization or prolongation of hospitalization in the absence of a precipitating, clinical adverse effect (e.g., for a preexisting condition not associated with a new adverse effect or with a worsening of the preexisting condition; admission for a protocol-specified procedure) is not, in itself, a serious adverse effect. The following definitions for rating severity of adverse events will be used:

Mild: Awareness of signs or symptoms, but easily tolerated; are of minor irritant type; causing no loss of time from normal activities; symptoms would not require medication or a medical evaluation; signs or symptoms are transient.

Moderate: Interferes with the subject's usual activity and/or requires symptomatic treatment.

Severe: Symptom(s) causing severe discomfort and significant impact of the subject's usual

activity and requires treatment.

AEs or SAEs will also be classified as to their relationship to the device, as follows:

Not Related: The event is due to an underlying or concurrent illness or effect of another device, drug or intervention and is not related to the investigational device, procedure or general surgery.

Possible: The event has a strong temporal relationship to the use of the investigational device, procedure or general surgery, and an alternative etiology is equally or less likely.

Probable: The event has a strong temporal relationship to the use of the investigational device, procedure or general surgery and another etiology is unlikely or significantly less likely.

Definite: An event that can only be attributed to the use of the investigational device, procedure or general surgery.

Not Assessable: The event's relationship to the use of the investigational device, procedure or general surgery cannot be assessed.

If an AE or SAE is determined to be probably or definitely related to the investigational device and has not been previously anticipated, the clinical finding would further be classified as an unanticipated adverse device effect (UADE). A UADE is defined as "any serious adverse effect on health or safety or any life-threatening problem or death caused by, or associated with, a device, if that effect, problem, or death was not previously identified in nature, severity, or degree of incidence in the investigational plan or application (including a supplementary plan or application), or any other unanticipated serious problem associated with a device that relates to the rights, safety, or welfare of subjects."

SAEs that are determined to be probably or definitely related to the investigational device are referred to as device-related serious adverse events (DRSAEs). The protocol definitions for "device failure", "device malfunction", and "technical observation" are provided below:

Device Failure: A device has failed if it does not perform according to the Instructions for Use provided with the device and as a result, negatively impacts the treatment, when used according to this protocol. A device failure that causes or contributed to a serious adverse event would be classified as a DRSAE.

Device Malfunction: A device malfunction is an unexpected change to the device that is not contradictory to the labeling and may or may not affect the performance of the device. A device malfunction is not considered to be a DRSAE unless it causes or contributes to a serious adverse event. **Technical Observation:** Malfunction or complaint with a medical device that has the potential to, but may or may not result in, a negative clinical consequence to the patient.

Note: A device failure or device malfunction is considered to be a DRSAE if it causes or contributes to a SAE.

Any Device Failure, Device Malfunction or Technical Observation must also be documented in the CRFs.

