4.3.2 Primary Safety Endpoint

Assessment of Adverse Events (incidence, relationship to device and severity) compared to the control arm and the medical literature.

Adverse events will be compared to the control therapy.

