5.5.3 Index Procedure

Once enrolled, each patient will be randomized into either the EndoRotor® mucosal resection arm or the control ablation arm. Randomization will occur within 2 weeks of the procedure. The investigators shall follow the technique described by the manufacturer's instructions as provided in the Instructions for Use.

Endoscopic treatment of the esophagus will be performed within 6 weeks of enrollment with outpatient video documentation of the residual Barrett's changes during upper endoscopy.

EndoRotor® Arm: At this point, the EndoRotor® will be set-up and used to resect the mucosa and submucosa to remove all gross visible disease. Lesions will be "lifted" using saline solution with dye such as Indigo carmine or Methylene Blue. Indelible ink (such as SPOT) will be injected into the region of the resection to identify the site after resection. If the lesion is circumferential, the endoscopist shall resect no greater than 270 degrees of the radial circumference of the esophagus to avoid stricture formation. The resection is taken down to the muscularis propria layer to ensure all of the mucosa and submucosa is removed in the area of persistence.

The EndoRotor® is set to either High Speed (1700 RPM) or low speed (1000 RPM) based on user preference and the vacuum is set to between 250 mmHg and 350 mmHg of negative pressure. The endoscopist will start the EndoRotor® motor using the left foot pedal, and will activate the cutting by depressing and holding the

right pedal down for as long as he wants to resect tissue. The procedure is repeated until the entire gross visible lesion has been removed down to the muscularis propria without entering the muscle layer. The specimen can be sent to Pathology by removing the filter in the specimen trap. A new filter is placed in the specimen trap allowing multiple lesions to be treated and analyzed histopathologically.

Continued Ablative Therapy Arm: The investigator shall exercise standard of care for continued ablative therapies namely RFA (HALO 90/60) and/or cleared cryotherapy devices. These will constitute two control devices. The investigator will choose the system in this arm. Operation of the each system will be done according to the manufacturer's instructions for use. The type of system used will be indicated on the case report forms.

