10.5 Reporting of Adverse Events

All adverse events, including SAE's and UADE's, will be monitored from the time of enrollment through the study exit. A description of the event, including the start date, resolution date, action taken, and the outcome shall be provided, along with the Investigator's assessment of the relationship between the AE and the study device and procedure.

All AE's should be followed until the event is resolved or judged to be clinically stable. The clinical site should plan to provide additional, relevant AE follow-up information to the Sponsor upon request.

All SAEs, DRSAEs, and UADE's must be reported to the Sponsor and/or CRO and the primary Investigator at the site **within 24 hours** of the Investigator becoming aware of the event. Additionally, the Investigator should notify their IRB, and local/national authorities as required, within their specified timeframes. The Sponsor and CRO will decide whether all of the local Investigators need to be informed immediately, or whether this can be postponed until the next regularly scheduled study update.

A completed SAE CRF **must** be uploaded to the Sponsor's secure web server **within 48 hours of the event**. The minimum required data to be recorded for an SAE includes: date of event, type of event, duration of event, severity, seriousness, action taken, outcome, causality and relationship to the Interscope device and procedure. In the case of a DRSAE, whenever possible, the device involved in the failure or malfunction is to be returned to Interscope for analysis.

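### The causality scale never names the control devices, so the relationship-to-device part of the primary safety comparison is not like for like between arms

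*Combined protocol and SAP*

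**What the plan says.** Section 4.3.2 defines the primary safety endpoint as "Assessment of Adverse Events (incidence, relationship to device and severity) compared to the control arm and the medical literature". Relatedness is one of its three named dimensions, and the comparator is the control arm.

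Section 10.4 supplies one scale for all events in both arms: "AEs or SAEs will also be classified as to their relationship to the device, as follows". Its categories share the same three anchors. Definite, for instance, is "An event that can only be attributed to the use of the investigational device, procedure or general surgery". Not Related covers underlying or concurrent illness, or an event that is the "effect of another device, drug or intervention and is not related to the investigational device, procedure or general surgery".

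Section 5.5.3 says of RFA and cryotherapy: "These will constitute two control devices". Neither is named anywhere in the scale.

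The derived terms follow the same pattern. Section 10.4 states: "SAEs that are determined to be probably or definitely related to the investigational device are referred to as device-related serious adverse events (DRSAEs". The minimum SAE data in Section 10.5 include "causality and relationship to the Interscope device and procedure". The general adverse event text in the same section uses a third anchor, the Investigator's "assessment of the relationship between the AE and the study device and procedure", without saying what the study device is in the control arm.

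Section 7.7 compares the rate of bleeding, perforation and stricture by a two-tailed Fisher test at 0.05. It names no relatedness category, although it introduces these events as complications due to treatment.

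**The concern.** A comparison of relatedness between arms needs the same question asked in each arm. Here the question is worded for the EndoRotor arm. A control subject has no Interscope device, and the RFA or cryotherapy device is, on a plain reading, another device, which is wording found under Not Related. A stricture after EndoRotor and the same stricture after RFA could then receive different ratings for reasons that have nothing to do with the injury.

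What is at stake is one named component of the primary safety endpoint. It also bears on what the data monitoring committee sees, because Section 10.2 asks for reports on a significant safety difference between EndoRotor and the control devices and on whether to continue. If control events are under-attributed, EndoRotor would look worse than it is.

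**Working it through.** No figure in the plan depends on the causality scale, so there is none to reproduce. The check is of the text, followed by an illustration of size.

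**Step 1: one event, two readings.** Take an RFA stricture in a control subject.

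| Item | If procedure means only the investigational procedure | If procedure includes the ablation |
|---|---|---|
| Section 10.4 scale | Effect of another device, unrelated to any anchor: Not Related | Linked to the procedure: Possible, Probable or Definite |
| Device-related SAE, main definition | Does not qualify | Does not qualify; the definition cites the investigational device alone |
| Section 10.5 SAE item | No Interscope device was used | Answerable for the procedure only |

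The text does not settle whether the word investigational carries over to procedure. The wider reading brings the event into the scale but does not make device-related SAE counts symmetric. Under either reading the scale gives one rating for device and procedure together, so it cannot isolate the relationship to device that Section 4.3.2 compares.

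**Step 2: how many events.** Section 1.3 gives RFA stricture 5% and bleeding 1%. Enrollment of 120 at 1:1 gives 60 per arm. Assuming no overlap between the two event types, 60 × (0.05 + 0.01) = 3.6 control subjects.

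**Step 3: the extreme split.** Suppose both arms have x true events out of n, all EndoRotor events are scored related and no control event is. For x against 0 with equal arms, the two-sided Fisher p is 2 × C(n, x) / C(2n, x).

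- 4/60 against 0/60: 2 × (60·59·58·57)/(120·119·118·117) = 2 × 0.0594 = 0.119
- 5/60 against 0/60: 0.057
- 6/60 against 0/60: 0.027

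Six of 60 is a 10% rate, which is an assumption above the documents' 6%.

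**Step 4: chance of a false finding.** This uses 55 evaluable subjects per arm, equal true rates in both arms, all EndoRotor events scored related, and exact enumeration of the two-tailed Fisher test at 0.05. The entries are the probability that related events appear significantly more frequent with EndoRotor.

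| True rate in both arms | No control events scored unrelated | Half | All |
|---|---|---|---|
| 6% (5% + 1%) | 0.6% | 2.6% | 11.1% |
| 10% (assumed) | 1.0% | 7.5% | 47.6% |

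With no control events counted, significance needs six or more EndoRotor events (6/55 against 0/55, p = 0.027; 5/55 against 0/55, p = 0.057). The plan specifies no such test on related events, so the table shows how far attribution alone could move a relatedness comparison. It does not give the error rate of a planned analysis.

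**The case against.** The strongest reply is that the scale is not confined to the investigational device. Every category also lists procedure and general surgery, and Not Related requires that the event be unrelated to those as well. The protocol uses procedure for both arms: Section 4.5 speaks of an EndoRotor or continued ablative therapy procedure, Section 5.5.3 describes both treatments under the index procedure, and Appendix 1 has a single procedure row for the two. On that usage an ablation stricture is procedure-related. This stands. A reader might infer that control-arm injuries must be scored Not Related, or that related events can occur in only one arm by definition. The text permits a Not Related score but does not force it.

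A reader might also infer that a control injury could never be a device-related SAE. That goes too far. The device-failure definition in Section 10.4 makes the failure of a device that causes or contributes to an SAE a device-related SAE, without limiting it to EndoRotor. An ablation injury without device failure still falls outside the main definition. Section 7 plans no comparison of device-related SAE counts.

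Third, events are adjudicated by an independent committee under a charter. The charter and case report forms are not among the documents and may contain arm-neutral instructions. The protocol itself supplies none, so adjudication cannot be assumed to cure the wording.

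Finally, stricture and bleeding are the events the Section 7.7 test counts, and that test names no relatedness filter. This also stands and limits the point to relatedness.

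**Conclusion.** The relatedness component of the primary safety comparison is not interpretable as written. The same control injury can be rated differently depending on a site's reading, and the main device-related SAE definition and the SAE form item are asymmetric between arms. The likely direction is against EndoRotor, so this would not manufacture a favourable safety claim.

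It would be tempting to conclude that the whole safety comparison with control is invalid. The documents do not support that. Incidence and severity do not use the scale. Nor does the Section 7.7 Fisher test, unless its reference to complications due to treatment is applied as a relatedness filter, which the plan leaves open.

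The size is modest at the documents' own rates: about 3 to 4 of 60 control subjects, and p = 0.12 at 4/60 against 0/60. The p = 0.027 result needs an assumed 10% rate and every control event scored unrelated. The rates in Section 1.3 describe RFA generally, no cryotherapy complication rate is given, and the share of events that sites would misattribute is unknown. This should be fixed, preferably before enrollment, because attributions are hard to reconstruct later. It does not undermine the trial's formal safety test.

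**What to change.** - In Section 10.4, anchor all five categories to the assigned study treatment device (EndoRotor, RFA or cryotherapy) and to its procedure, rated as two separate items in both arms.
- Limit the reference to another device under Not Related to devices that are not study treatments.
- Define device-related SAE for the assigned device in both arms, and change the SAE data item in Section 10.5 to match.
- Keep a separate EndoRotor-only flag for unanticipated adverse device effect reporting.
- State in Section 7.7 that bleeding, perforation and stricture are counted regardless of attributed relatedness.

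The cost is definition wording and one extra attribution item per event on the case report form at each site. It needs no added visits and no change in sample size.

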10.5 Reporting of Adverse Events

All adverse events, including SAE's and UADE's, will be monitored from the time of enrollment through the study exit. A description of the event, including the start date, resolution date, action taken, and the outcome shall be provided, along with the Investigator's assessment of the relationship between the AE and the study device and procedure.

All AE's should be followed until the event is resolved or judged to be clinically stable. The clinical site should plan to provide additional, relevant AE follow-up information to the Sponsor upon request.

All SAEs, DRSAEs, and UADE's must be reported to the Sponsor and/or CRO and the primary Investigator at the site **within 24 hours** of the Investigator becoming aware of the event. Additionally, the Investigator should notify their IRB, and local/national authorities as required, within their specified timeframes. The Sponsor and CRO will decide whether all of the local Investigators need to be informed immediately, or whether this can be postponed until the next regularly scheduled study update.

A completed SAE CRF **must** be uploaded to the Sponsor's secure web server **within 48 hours of the event**. The minimum required data to be recorded for an SAE includes: date of event, type of event, duration of event, severity, seriousness, action taken, outcome, causality and relationship to the Interscope device and procedure. In the case of a DRSAE, whenever possible, the device involved in the failure or malfunction is to be returned to Interscope for analysis.

10.6 Privacy and Confidentiality

Privacy and confidentiality of subjects will be maintained throughout the Interscope ENDOROTOR trial. A unique identification code will be assigned to each patient participating in this trial. Access to the patient's medical records will be limited to authorized personnel of the Sponsor, their designated CRO, clinical site study staff and authorized regulatory authorities as required by the EC and/or local or national agencies. Any data that may be published in abstracts or scientific journals, and/or presented at medical meetings will reference a unique patient code and will not reveal the patient's identity. The Sponsor and their representative (CRO) will make every reasonable effort to protect the confidentiality of the subjects participating in this study.

11.0 STUDY DATA REPORTING AND PROCESSING

11.1 Data Entry, Cleaning and Editing

Development of a validated database for the trial will be performed by Interscope and/or its CRO. Interscope will also be responsible for auditing the database and confirming the overall integrity of the data.

Single data entry into the database will be done by Interscope and/or its CRO. All study records and CRFs will be subjected to initial inspection during routine monitoring visits for omitted data, gross data inconsistencies, and deviations. Any deficiencies or deviations will be resolved by the site. Any discovered errors are referred to the clinical site research coordinator for correction through a Data Clarification Form.

11.2 Final Data Analyses

All exported datasets for analyses by SAS will undergo a final data cleaning procedure using SAS programmed logical routines unique to each exported dataset.

APPENDIX 1 – SCHEDULE OF STUDY ASSESSMENTS

A schedule of study assessments is provided below.

| | Baseline (≤14 days) | Index Procedure (Day 0) ³ | Discharge | 3 Months (±14 days) | 6 Months (±14 days) ³ | 9 Months (±14 days) ⁴ |
|---|---------------------------|--|-----------|---------------------------|--|--|
| Confirm Eligibility | X | X | | | | |
| Informed Consent | X | | | | | |
| Randomization | X | | | | | |
| Demographics | X | | | | | |
| Medical History | X | | | | | |
| Physical Examination | X | | | | | |
| Pregnancy Test ¹ | X | | | | | |
| EndoRotor® or Continued Ablative Therapy Procedure | | X | | X | X ⁴ | X ⁵ |
| Surveillance Biopsies | | X | | X | X ⁴ | X ⁵ |
| Adverse Event Assessment | | X | X | X | X ⁴ | X ⁵ |
| Analog Pain Scale ² | | X | X | X | X | X |

¹ Urine pregnancy test for female of child bearing potential within 1 day of procedure.

² Pain assessment should be completed just prior to each endoscopic procedure and at discharge.

³ The index procedure must be done within 6 weeks of enrollment with outpatient video documentation of the residual Barrett's changes during upper endoscopy.

⁴ The exam at day 6 months is not required if there is no presence of intestinal metaplasia (Barrett's) on biopsies from the preceding exam.

⁵ The exam at day 9 months is not required if there is no presence of intestinal metaplasia (Barrett's) on biopsies from the preceding exam. See Section 5.7 Subject Follow-up.

